1.5 Data Analysis

As the purpose of this research study is to assess the interaction between O₃ exposure and cardiorespiratory function during rest and exercise in healthy athletes, we aim to characterise the relationship between resting response and exercise response, as well as assess the effects of ozone exposure on pulmonary function, ventilatory patterns and exercise parameters. To assess susceptibility to exercising O₃ response, a regression analysis will occur between the reduction in spirometry values post 2-hours resting exposure at 750ppb and the reduction in spirometry values post-O₃ condition exercise trial. It is hypothesized that greater decrements in FEV1, FVC, FEF₂₅₋₇₅ and PEFR will occur following exercise under O₃ exposure in subjects who also exhibited greater expiratory flow limitations following resting exposure.

Page 11 of 23

Examining ventilatory patterns during exercise is another primary objective of the proposed research study. By comparing tidal volume, breathing frequency, and inspiratory capacity throughout the constant work-rate exercise bout between the two experimental conditions through mixed models, further insight into how O₃ exposure may impact ventilation may be gained.

Analyzing time to exhaustion (in seconds) for the maximal constant work-rate exercise bouts between the two experimental conditions will also be assessed by mixed models. Potential differences between the two conditions will help elucidate whether performance changes occur due to O₃ exposure. Further analysis of ratings of perceived exertion, dyspnea, and FeNO via mixed models will also occur between the two experimental trials.

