Sample size was calculated using data from previous studies that examined changes in FEV1 in athletes following ozone exposure during exercise. A similar crossover design in elite athletes utilizing ozone exposure at 200ppb found a 0.95-litre reduction in FEV1 following exercise, with a standard deviation of post-exercise measures of 0.86-litres (Gong et al., 1986). Calculation for a crossover design based on analysis of variance F-tests using these values with a power of 0.8 and an alpha level of 0.05 led to a sample size of 15 subjects. Sample size will be increased to 24 to include female subjects.

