The second visit will consist of resting exposure to ozone and pulmonary function tests. Subjects will conduct pre-ozone resting spirometry, FeNO, dyspnea, and symptom measurements, followed by 2-hours of resting O₃ exposure at 750ppb. During the resting exposure, subjects will be seated with a three-way non-rebreathe valve and mouthpiece connected via tube to the ozone chamber. Nose-clips will be worn for the entirety of the protocol, and expired volumes will be analyzed to determine average minute ventilation, and effective dose of O3 (minute ventilation x O₃ concentration x exposure duration) (Silverman et al., 1976). Subjects will be permitted to use personal electronic devices (phone, laptop, tablet etc.) during exposure, provided no significant movement is required. Following exposure, subjects will complete identical spirometry, FeNO, symptoms, and dyspnea measurements immediately and 30-minutes post-exposure to that completed pre-exposure. Post-exposure and pre-exposure values will be compared to determine resting response to O3.

The third and fourth visits will consist of identical procedures, randomized as to the order of the O3 and control conditions. During both experimental trials, a lab member other than the researcher will control the O₃ concentration in order to maintain blinding of the participant and the researcher as to the condition. During the O₃ exposure, subjects will receive 170ppb O₃, and during the control exposure subjects will receive room air (typically <10ppb O₃). Upon arrival in the laboratory, the researcher will confirm that pre-visit requirements (detailed above) are met, prior to resting spirometry, FeNO, symptoms, and dyspnea measurements. Subjects will then be connected via tube and mouthpiece/valve to the O₃ chamber. While remaining connected to the O₃ chamber, participants will then complete a standardized warmup on the Velotron of 25-

Page 10 of 23

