minutes at 10% below previously established aerobic threshold. Subjects will then be provided with 5-minutes of rest prior to completing 30-minutes at 10% below anaerobic threshold. Expired gas and volumes will be analyzed throughout the trial, and participants will perform an inspiratory capacity test, have blood lactate sampled via finger-prick, rate their perceived exertion and dyspnea every 10-minutes (10,20,30-minutes into exercise). Post-exercise, subjects will remove their mouthpiece and complete spirometry, FeNO, dyspnea, and symptoms testing (~5mins), prior to reattaching the mouthpiece and completing a time-to-exhaustion test at 105% of peak power achieved during the GXT. Strong verbal encouragement will be provided to subjects, and exercise will be stopped when they are no longer able to maintain 60 RPM, and time-to-exhaustion will be recorded. Post-exercise, a final set of pulmonary function, symptoms, and dyspnea testing will occur at 30-minutes following completion of the submaximal exercise bout.

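### Does leaving the scale of the spirometry reduction open, with no dose term, undermine the rest-to-exercise regression?

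*Combined protocol and SAP*

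**What the plan says.** Section 1.5 contains the only description of this analysis: "a regression analysis will occur between the reduction in spirometry values post 2-hours resting exposure at 750ppb" and the reduction after exercise under ozone, for FEV1, FVC, FEF25-75 and PEFR. The hypothesis is that larger exercise decrements will be seen "in subjects who also exhibited greater expiratory flow limitations following resting exposure". No unit, scale or covariate is given. On the resting visit, section 1.4 Procedures adds only that "Post-exposure and pre-exposure values will be compared to determine resting response to O3".

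Inhaled-dose data are collected. At Visit 2, "expired volumes will be analyzed to determine average minute ventilation, and effective dose of O3"; at Visits 3 and 4, "Expired gas and volumes will be analyzed throughout the trial". Section 1.5 uses neither as a covariate in the regression. Section 1.1 Sample and Recruitment addresses dose by design: its VO2max criterion is meant to narrow the spread of ventilation, and so of effective dose, between participants.

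The only spirometry change given with a unit is in the sample-size paragraph of section 1.1, where an earlier crossover study at 200 ppb "found a 0.95-litre reduction in FEV1 following exercise, with a standard deviation of post-exercise measures of 0.86-litres". The same paragraph ends: "Sample size will be increased to 24 to include female subjects".

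**The concern.** If reductions are analysed in litres and loss scales with lung size, a person with large lungs tends to lose more at both visits. Men and women differ in lung size, so mixing the sexes widens that shared component. The slope can then move in the hypothesised direction even when sensitivity at rest is unrelated to sensitivity in exercise. Shared dose can add to this on either scale if response follows inhaled dose, and a VO2max floor per kilogram does not equalise absolute ventilation between the sexes.

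At stake would be a false conclusion that a resting ozone test identifies athletes who respond in exercise. The ozone versus room-air comparisons are not affected.

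**Working it through.** **The plan's own figure.** A paired t calculation with difference 0.95 L, SD of the difference 0.86 × √2 = 1.216 L (within-subject correlation 0) and two-sided alpha 0.05 gives n = 15 with power 0.803. The stated 15 therefore reproduces. It concerns a mean FEV1 difference, not the regression, so its litre unit does not fix the regression's scale. FEF25-75 and PEFR are flows and could not be in litres in any case.

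**How variable is the response?** Inputs are 0.95 L and 0.86 L (section 1.1) and an assumed baseline SD b of 0.5 to 0.7 L. The CV of loss is √(0.86² − b²)/0.95, and log-SD is √ln(1 + CV²).
- b = 0.5: √0.4896/0.95 = 0.737, log-SD 0.66
- b = 0.6: √0.3796/0.95 = 0.649, log-SD 0.59
- b = 0.7: √0.2496/0.95 = 0.526, log-SD 0.49

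This is a rough guide. The SD of loss also contains lung-size and dose spread, so the true sensitivity spread could be somewhat smaller.

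**Correlation from lung size alone.** Let litre loss be baseline × fractional loss, with independent fractional losses at the two visits. Then r = c²/[c²(1 + k²) + k²], where c is the CV of baseline FEV1 and k the CV of fractional loss. Assume 15 men at 4.8 L, 9 women at 3.6 L and a within-sex SD of 0.5 L. The mean is (15 × 4.8 + 9 × 3.6)/24 = 4.35 L. The variance is 0.625 × 0.375 × 1.2² + 0.25 = 0.5875. So c = 0.766/4.35 = 0.176 and c² = 0.031.
- k = 0.5: 0.031/(0.0387 + 0.25) = 0.11; simulated false-positive rate 9%
- k = 0.75: 0.031/(0.0484 + 0.5625) = 0.05; 7%
- k = 1.0: 0.031/(0.062 + 1) = 0.03; 6%
- k = 0.25: 0.031/(0.0329 + 0.0625) = 0.32; 37%

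At n = 24 significance needs |r| above 0.40. Only the k = 0.25 case comes close, and it lies well below the CV of 0.53 to 0.74 found above.

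**Fuller simulation.** The table gives the percentage of null trials declared significant (two-sided 5% slope test, 12 men and 12 women), at log-SD 0.5 / 0.66. The adjusted model is percent change plus sex, Visit 2 effective dose and an exercise-dose term.

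| True pattern of loss | Litres | Percent change | Adjusted |
|---|---|---|---|
| Fractional loss follows absolute ventilation | 20.9 / 13.3 | 7.7 / 6.5 | 5.4 / 5.7 |
| Fractional loss follows ventilation per FEV1 | 7.9 / 6.5 | 7.1 / 6.6 | 6.3 / 5.9 |
| Fractional loss independent of dose | 8.5 / 7.1 | 5.0 / 5.2 | 5.0 / 5.3 |
| Litre loss unrelated to lung size or dose | 4.9 / 4.9 | 9.4 / 6.9 | 6.7 / 6.3 |

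Assumptions, none from the documents except the VO2max floors (men / women):
- mass 75±8 / 60±7 kg; FEV1 4.8±0.5 / 3.6±0.4 L; VO2max 65±4 / 58±3 ml/kg/min with floors 60 / 55
- resting ventilation proportional to mass (log-SD 0.12); exercise ventilation proportional to absolute VO2max (log-SD 0.10, plus 0.05 day to day)
- mean loss 12% (0.5 L in the last row); error 0.08 L per decrement; lognormal sensitivities
- 10,000 replicates per setting (5,000 in the last row)

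A 15/9 split gives 17.8 / 11.5 for litres in the first row and 6.5 to 8.2 in the second and third. At log-SD 0.4, below the derived range, litres in the first row reaches 33.4% and percent change in the last row 12.4%.

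**Cost of adjustment.** At a true correlation of 0.6, power is 72% to 77% for the unadjusted percent-change regression and 62% to 71% for the adjusted one, which uses three more residual degrees of freedom (22 to 19).

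**The case for a change.** The strongest argument for acting is not bias but freedom of choice. At log-SD 0.5 to 0.66 the two scales disagree on significance in 4% to 14% of null trials, and in 9% to 24% when the true correlation is 0.3 to 0.6, with four spirometry measures to choose among. Prespecifying a scale costs one sentence and needs no new data. Section 1.4 also leaves open which Visit 2 measurement defines the resting response, immediate or 30 minutes after exposure.

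Part of this stands: the text is under-specified, and a report should name the scale and time point used. It does not amount to a fault in the design or method. A true correlation of 0.3 lies below the 0.40 needed for significance at n = 24, so a significance verdict there is fragile under any reasonable analytic choice. The null disagreement also reaches its upper figures only where response follows absolute dose.

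The remedy of percent change plus a dose-adjusted model is weaker than it looks. Dividing both sides by baseline creates its own shared component when litre loss does not scale with lung size, as the last row of the table shows. The adjusted model contains no baseline lung function, height or mass, so it could not support a statement of independence from body size.

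**Conclusion.** No change follows. The missing scale is a detail that an analyst must settle to run the regression and can settle sensibly. Nothing in the plan commits it to litres, and the 0.95 L figure is a borrowed sample-size input for a different comparison. Under most assumptions either scale gives 5% to 9% false positives. The 12% to 21% figure for litres requires both that scale and a response that follows absolute dose.

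Omitting a dose term is a fair trade-off. The hypothesis asks whether resting responders are also exercise responders, and the unadjusted regression answers that. The plan claims no link independent of dose, it deals with dose partly through its VO2max criterion, and adjustment with 24 subjects costs roughly 6 to 10 points of power. Should a report later claim that the link is independent of dose or body size, that claim would need its own model with suitable terms.

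The conclusion rests on assumed physiology and on the variability inferred from the 200 ppb study. Much more uniform responses (k near 0.25) would make the choice of scale matter considerably more, in either direction.
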